# **Duration of study periods**

Participants will be dosed with study intervention over 12 weeks. This is a common duration of evaluation of AED's in clinical studies (EMA 2018, FDA 1981). After at least 55 participants in a cohort 1 and at least 45 patients in Cohort 2 have completed 4 weeks of treatment, an interim

unblinded review of all cumulative safety, PK and efficacy data of JNJ-40411813 available to that date will be performed to decide on the dose in the following cohort. If the results of the review are inconclusive, a second interim review of the same cohort may be done after the last participant has completed the 12-week visit.

Based on an evaluation of the variability of seizure count in prior epilepsy studies completed by the sponsor (Janssen, data on file), a baseline duration of 8 weeks was considered to give a more accurate and representative estimate of monthly seizure count than shorter periods.

The double-blind study period will be followed by a follow-up period of 2 weeks if the participant does not take part in the OLE period. The dose will not be tapered after completion of the double-blind study period. Although there are no signals of a rebound effect after stopping the treatment with JNJ-40411813 from preclinical studies or previous clinical studies, the change of seizure count after stopping the treatment will be investigated in the follow-up period.

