# 8.2.2. Baseline perioda

After screening, if they meet the in- and exclusion criteria for which data are available, participants can start the 8-week prospective pretreatment baseline period pending the results of the central laboratory and the adjudication process. However, when the results of these assessments indicate that the participant does not meet the in- and exclusion criteria, the participant will terminate the baseline period and will not be randomized to treatment.

When required for practical reasons, the baseline period may be up to 1 week longer or shorter than 8 weeks.

The participant and/or caregiver will be provided access to an (electronic) diary to record seizures. The e-diary will be an app downloaded on the smartphone owned by the participant. Only if the participant and/or caregiver do not own a smartphone, a smartphone programmed for the study will be provided.

During the baseline period, the participant will be contacted by phone by the investigator or study nurse to confirm correct use of the e-diary. This contact should take place at least 4 weeks after the start of the baseline period, but multiple contacts are allowed when required.

-

This section has been amended by Amendment INT-1

Participants must be compliant with the recording of information in the diary throughout the study. Seizures that will be entered during baseline and throughout the study include focal aware seizures with and without motor signs, focal impaired awareness seizures and focal to bilateral tonic-clonic seizures. Myoclonic, or other generalized seizures will not be entered.

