1.2. Study Design

This is a double-blind, randomized, parallel, placebo-controlled study with the option for an open-label extension (OLE) period. The study will consist of 1 to a maximum of 3 cohorts. In each cohort, for each participant the study consists of a screening visit, an 8-week prospective pretreatment baseline period, an up to 12-week double-blind treatment period and, for those participants electing not to enter the OLE period, a follow-up telephone visit 2 weeks after the last dose of study intervention. Participants have the option to enter an OLE period, in which treatment with JNJ-40411813 may be continued until the product becomes available by prescription, or until the development of JNJ-40411813 in this indication ceases. The total maximal duration of the study is approximately 22 weeks for each participant, up to the time of entry into the OLE period.

Participants from 18 to 69 years (inclusive) old with an established diagnosis of focal onset seizures will be enrolled in the study. For the first cohort, approximately 80 eligible participants will be initially enrolled to ensure that 60 participants are randomly assigned in a 2:1 ratio to receive either JNJ-40411813 twice daily (bid) or placebo. For each following cohort, approximately 60 eligible participants will be initially enrolled to ensure that 50 participants are randomly assigned in a 4:1 ratio to receive either JNJ-40411813 bid or placebo.

least 20% of the participants must be included in each of the two groups.

During the 8-week prospective pretreatment baseline period, participants will continue to take their prescribed AEDs (one of which must include levetiracetam or brivaracetam) without change in dosage(s); new concomitant AEDs should not be added. During the baseline period, participants will record seizure information (type and frequency of seizures) in an e-diary. Baseline monthly seizure count will be defined as the number of observable focal onset seizures recorded during the baseline period, multiplied by 28/ XBL, where XBL is the number of days comprising the baseline.

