5. STATISTICAL ANALYSES

5.1. General Considerations

Study Phases

There are five study phases defined in this study: Screening, Pre-treatment Baseline, Double-blind, Follow-up (post double-blind) and Open-Label Extension (OLE). Each analysis phase has its own analysis reference start date.

Screening Phase

Participants will have a screening visit immediately prior to the start of the pre-treatment baseline period, where the date of screening will be defined as the date written informed consent is obtained.

CONFIDENTIAL – FOIA Exemptions Apply in U.S.

Pre-treatment Baseline Phase

After screening, participants will start the 8-week prospective pre-treatment baseline period pending the results of the central laboratory and, if applicable, the adjudication process. If the results suggest the participant does not meet the in- and exclusion criteria, the participant will terminate the baseline period and will not be randomized to treatment.

During the pre-treatment baseline phase, participants will record seizure information in an e-diary. The pre-treatment baseline phase is defined as starting on the day of screening when the participant has initiated the e-diary and ends on the day of Visit 2 after the investigator enters the baseline period as completed in the diary dashboard.

Double-blind Phase

The analysis reference start date of the double-blind phase is the date of the first dose of the double-blind medication (i.e. Clinic Visit 2, Day 1). A participant will be considered to have completed the study if they complete the double-blind period up to Week 12, or have elected to exit after reaching the baseline monthly seizure count by Day 28 or after exceeding the monthly baseline seizure count during a moving 28-day interval after Day 28. In either case, participants should complete Visit 7 (Week 12/Early Withdrawal) and the reference end date of the double-blind phase is the Visit 7 date.

Follow-up Phase

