Participants who continued treatment to the end of the double-blind period (Week 12) or have completed the study (as defined above) and have not elected to participate in the OLE will go into the follow-up phase. In the follow-up phase, participants will continue to record only the number of seizures using the e-diary until 2 weeks after the last dose and will have a telephone follow-up visit at 2 weeks ± 2 days after the last dose. The analysis reference start date of the follow-up analysis phase is the day after the reference end date for the double-blind phase. The analysis reference end date of the follow-up analysis phase is the maximum of the telephone follow-up visit date or the e-diary follow-up date.

Open-Label Extension Phase

For participants electing to participate in the OLE, the reference start date of the OLE phase will be either the date of last study drug intake by the participant in the double-blind period for subjects who continue into the OLE without an interruption of ≤4 weeks from the double-blind period, or the date of the OLE baseline visit when there is an interruption of >4 weeks (i.e. the last visit of the double-blind period was more than 4 weeks ago). Participants participating in the OLE without an interruption of ≤4 weeks from the double-blind period will not have the follow-up visit (Visit 8), and those with an interruption of >4 weeks will complete the follow-up visit. The analysis reference start date for the OLE phase is the date of the last dose taken in the double-blind phase. The analysis reference end date of the OLE phase is either the date when the last dose of study drug is taken in the OLE phase (Visit OLE11), the date OLE is stopped by the sponsor or the date of early withdrawal from the OLE phase. The open-label efficacy data will be summarized by the double-blind treatment group in the form of an intervention sequence (PBO/JNJ and JNJ/JNJ).

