5.5.2.2. Analysis Methods

To evaluate the CCI , descriptive statistics (N, mean, standard deviation, median, minimum, and maximum) for actual values for the weekly seizure count during each study period (baseline, double-blind and follow-up) will be provided by treatment group (JNJ-813) pooled over CCI , and also treatment group by CCI

for all observable focal-onset seizures. Mean (\pm SE) plot for the weekly seizure count will be provided for each week by treatment group and by stratum.

Furthermore, the following additional safety findings will be reported:

- for each cohort the number and percentage of participants with cluster seizures will be summarized by treatment group (JNJ-813) pooled over treatment group by GCI within each study period (baseline, double-blind and follow-up).
- for each cohort the number and percentage of participants in the follow-up period with focal to bilateral tonic-clonic seizures who had none reported in the baseline or double-blind period will be summarized by treatment group (JNJ-813) pooled over and also treatment group by
- for each cohort the number and percentage of participants in the follow-up period with a seizure rate that is more than twice that of the baseline monthly seizure count will be summarized by treatment group (JNJ-813) pooled over treatment group by The follow-up monthly seizure count is defined as the total number of observable focal onset seizures occurring during the follow-up period, multiplied by 28/X_{FU}, where X_{FU} is the number of days comprising the follow-up period.

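### The cluster-seizure summary in SAP 5.5.2.2 takes no account of days observed, so the 14-day follow-up will look better than baseline even if nothing has changed

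*SAP*

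**What the plan says.** SAP 5.5.2.2 ends with three additional safety findings. The first is that, per cohort, "the number and percentage of participants with cluster seizures will be summarized by treatment group", shown "within each study period (baseline, double-blind and follow-up"). It mentions no rate, common window or days observed. The third item counts participants whose follow-up seizure rate is more than twice baseline, and it does scale follow-up seizures, by 28/X_FU.

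The three periods differ in length:
- SAP 1.2 has "an 8-week prospective pretreatment baseline period, an up to 12-week double-blind treatment period", and Protocol 8.2.2 adds that "the baseline period may be up to 1 week longer or shorter than 8 weeks".
- Double-blind may be cut short. Under SAP 5.1, participants who "have elected to exit after reaching the baseline monthly seizure count by Day 28" count as completers, as do those who exit after exceeding that count in a later 28-day interval.
- In follow-up, participants record seizures "using the e-diary until 2 weeks after the last dose" (SAP 5.1). Those who elect to enter the open-label extension do not go into this phase.

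On purpose, Protocol 4.2 (Duration of study periods) says that "the change of seizure count after stopping the treatment will be investigated in the follow-up period". SAP 5.3.1 counts a cluster as one seizure.

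**The concern.** Whether a participant has had any cluster is a cumulative outcome: the longer the observation, the more likely a yes. The plan allows for this elsewhere, scaling baseline, double-blind, follow-up and open-label seizure counts to 28 days. The cluster item is laid out over three periods of very different length without doing so.

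What is at stake is how a withdrawal-safety display is read. Someone looking along the row from baseline to follow-up would see a fall that comes from the shorter window, and a real increase in clustering after stopping could sit behind it. In the readable text this is the only output specific to clustering after the last dose.

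**Working it through.** **Period lengths.** Baseline is 8 weeks = 56 days (49 to 63 allowed), double-blind up to 12 weeks = 84 days, and follow-up 2 weeks = 14 days. Check against SAP 1.2: 8 + 12 + 2 = 22 weeks, which agrees with "The total maximal duration of the study is approximately 22 weeks for each participant". The plan states no expected cluster percentage, so there is none to reproduce.

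**Assumption.** The documents give no cluster rate. I take 0.1 to 1 cluster per 28 days, constant over time and the same for everyone, with Poisson occurrence. For rate r per 28 days and T days observed, P(at least one cluster) = 1 − exp(−rT/28).

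**No true change, full-length periods:**

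| r per 28 days | 56 d | 84 d | 14 d |
|---|---|---|---|
| 0.1 | 18.1% | 25.9% | 4.9% |
| 0.25 | 39.3% | 52.8% | 11.8% |
| 0.5 | 63.2% | 77.7% | 22.1% |
| 1 | 86.5% | 95.0% | 39.3% |

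For example, at r = 0.25: 1 − exp(−0.5) = 39.3%; 1 − exp(−0.75) = 52.8%; 1 − exp(−0.125) = 11.8%. Across the permitted baseline of 49 to 63 days, the baseline figure at 0.25 runs from 35.4% to 43.0%.

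**Heterogeneity.** If rates vary between participants as a gamma with mean m and shape k, P = 1 − (1 + mT/(28k))^(−k). At m = 0.25, k = 0.2 gives 22.2% / 26.8% / 9.3%, and k = 0.5 gives 29.3% / 36.8% / 10.6%. The effect is smaller but in the same direction.

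**Hidden worsening, common rate.** At r = 0.25, a doubled rate in follow-up shows 22.1% and a tripled rate 31.3%, both below the 39.3% at baseline. Since only rT enters the formula, the rate must rise 56/14 = 4-fold to match the 56-day baseline percentage, whatever r is.

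**Early exit.** If a fraction f leaves at day 28, the double-blind percentage equals baseline when f = (P84 − P56)/(P84 − P28). At r = 0.25 this is (52.8 − 39.3)/(52.8 − 22.1) = 0.44. For r = 0.1, 0.5 and 1 it is 0.48, 0.38 and 0.27. Above these fractions the apparent rise from baseline to double-blind becomes a fall. Follow-up stays lower either way: at r = 0.25, a 28-day stay gives 22.1% against 11.8% in 14 days, and the comparison with baseline does not involve exits.

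**Equal windows.** In 14-day windows an unchanged rate gives equal percentages (11.8% at 0.25; 22.1% at 0.5), and a doubling after stopping shows as a rise (11.8% to 22.1%; 22.1% to 39.3%).

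**The case against.** The strongest reply is that the item specifies a descriptive table by arm within period, with no planned between-period difference, test or decision rule. Between arms inside baseline or follow-up, length does no harm. The Protocol 4.2 sentence concerns seizure counts rather than clusters, and parts of SAP 5.5.2 are redacted, so its purpose cannot be read in full. All of that is right. Even so, three periods shown together, in a section on participants followed after their last dose, invite a reading across them.

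The section's weekly counts and its 28-day-scaled follow-up rate also cover much of the ground, because each extra cluster episode adds to them. A reader should therefore not infer that worsening after withdrawal would go unseen altogether. What those measures miss is isolated seizures turning into clusters, because a cluster counts as one seizure.

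Two further inferences are tempting but unsupported. One is that the table will show a rise on treatment; that depends on how many leave early, which the documents do not give, and continuing double-blind after reaching the baseline count is allowed. The other is that early exits fall mainly on placebo and so bias the double-blind arm comparison. No passage says so, and Protocol 4.2.1 calls efficacy unknown. That comparison is affected only if exit differs by arm.

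The rates are also assumed. Exclusion criterion 3 removes participants whose seizures cannot be counted accurately, with extreme clustering as one example, which argues against the upper end of the range.

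**Conclusion.** The point holds for the follow-up column. With no true change in the same participants, the percentage with a cluster will be lower in follow-up than in the earlier periods. Under a common constant Poisson rate of 0.1 to 1 per 28 days, the drop from baseline is from 18% to 5% at the low end and from 86% to 39% at the high end. With strong heterogeneity at mean 0.25 it is from 22% to 9%. The 4-fold multiple rests on the common-rate model and a 56-day baseline, but not on the rate chosen.

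Follow-up also leaves out those who elect the open-label extension, so the denominator changes between periods. That can move the percentages in either direction, separately from length.

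This is a cheap improvement to a descriptive safety output. No test is affected, and the primary analysis is unchanged.

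**What to change.** Rewrite the one item in SAP 5.5.2.2. For participants who enter follow-up, report by arm either:
- the percentage with a cluster in equal 14-day windows: baseline windows and the follow-up, with the last 14 double-blind days as a further reference and a note that exits triggered by seizures select a high-count window; or
- cluster episodes per 28 days, with the within-participant change from baseline.

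Keep the whole-period percentages only beside denominators and days observed.

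The cost is a little more programming on e-diary data already collected; no visit or procedure changes. The drawback is noise: in 14 days each cluster scales to 28/14 = 2 per 28 days, so follow-up rates move in steps of 2. The equal-window percentages avoid that scaling but still rest on 14 days per participant.

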# 6.5. Concomitant Therapyb

All prestudy therapies administered up to 30 days before screening must be recorded at screening (and confirmed by treating physician).

During the 8-week prospective pretreatment baseline period and during the 12-week double-blind treatment period, participants will continue to take their prescribed AEDs (one of which must include levetiracetam or brivaracetam) without change in dosage(s); new concomitant AEDs should not be added. For the concomitant AEDs including levetiracetam or brivaracetam, all doses within the limits of current clinical practice will be allowed. Concomitant AEDs will not be provided by the study sponsor.

Two exceptions to this rule will be allowed:

<sup>a This section has been amended by Amendment INT-1

[figure not shown]
b This section has been amended by Amendment INT-1

- Based upon clinical judgment, a one-time dosage adjustment of concomitant AEDs is permitted to mitigate adverse events attributable to those AEDs. Collection of blood for plasma concentration of these AEDs is allowed, at the discretion of the investigator.
- One-time changes in AED dosages do not represent a change in the daily AED regimen. For example, if the participant took an extra dose of an AED on one day, this would not represent a change in the daily AED regimen.

Rescue medication may be used as needed (PRN). Each administration of rescue medication must be documented in the seizure e-diary. However, benzodiazepines or barbiturates received on a continuing basis at stable dosages for 1 month before screening should be considered as concomitant AEDs. Benzodiazepines or barbiturates used as sleep aid or to treat anxiety will be allowed but should be documented in the eCRF.

For levetiracetam or brivaracetam drug intake on the days of study visits, the same rule applies as for JNJ-40411813: On the day of Visits 2, 4, 6 and 7 CCI will be taken in the study center during the study visit and CCI. Dosing during the site visit will be witnessed by the study staff. CCI. Participants taking levetiracetam XR should preferably take their medication in the morning and take this medication in the clinic during Visits 2, 4, 6 and 7. If the participant takes levetiracetam XR in the evening, this should not be changed for the study.

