# 6.7. Intervention After the End of the Studya

Investigators may re-contact the participant to obtain follow-up information regarding the participants' safety if there are any safety concerns at the last study visit.

Participants should continue taking the AEDs they were using during the study until such time as changes in their treatment are recommended by their treating physician. Changes in their treatment for epilepsy will be allowed when required during the follow-up period.

The sponsor has added an OLE period to this study (to be initiated when all required supplies are available), with eligibility for all participants who completed the double-blind study period and experienced no safety concerns.

<sup>a This section has been amended by Amendment INT-2

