## 8.2.4. Follow-up/Early Withdrawal Visit

For participants who will participate in the OLE period, no follow-up visit will be performed. For details see Section 10.4.

All participants who discontinue the study before Week 12 are encouraged to complete the early withdrawal visit (Visit 7, Week 12/Early Withdrawal). The procedures to be completed during this visit are listed in the SoA. Participants who complete all study visits (including Visit 7) will have a follow-up telephone call with the investigator to review AEs and health status.

Participants who continued treatment to the end of the double-blind treatment period (Week 12) or have completed the study as per Section 7.2 will continue to collect information on the number of seizures they experience using the e-diary until 2 weeks after the last dose of study medication. Participants can start treatment with a new AED when required during the follow-up period.

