6.5. Appendix 5 Prior and Concomitant Medications

Prior and Concomitant medications will be coded using the World Health Organization Drug Dictionary (WHO-DD). Prior medications are defined as any therapy used before the day of first dose (partial or complete) of study intervention. Concomitant medications are defined as any therapy used on or after the same day as the first dose of study intervention, including those that started before and continue on after the first dose of study intervention.

Summaries of concomitant medications will be presented by ATC term, cohort and treatment group for the double-blind and open-label phases for the SAF and SAFOLE analysis sets. The proportion of participants who receive each concomitant medication will be summarized as well as the proportion of participants who receive at least 1 concomitant medication.

Prior medications will be summarized by treatment group, cohort and ATC term.

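### Follow-up seizure counts are compared with baseline over all days although AEDs may be added in follow-up, and no planned table shows who changed AED, so a treated rise can read as no rise

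*SAP*

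**What the plan says.** Protocol 4.2 (Duration of study periods) says that the dose is not tapered and that "the change of seizure count after stopping the treatment will be investigated in the follow-up period". SAP 5.1 sets the length: "participants will continue to record only the number of seizures using the e-diary until 2 weeks after the last dose". Week 12 completers and participants who exit early on seizure count are followed, unless they enter the OLE (SAP 5.1, 5.5.2.1).

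During baseline and double-blind treatment, prescribed AEDs stay unchanged apart from limited exceptions, and "new concomitant AEDs should not be added" (Protocol 6.5). Follow-up is different. Protocol 8.2.4: "Participants can start treatment with a new AED when required during the follow-up period". Protocol 6.7: "Changes in their treatment for epilepsy will be allowed when required during the follow-up period".

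SAP 5.5.2.2 defines the follow-up rate without reference to AED changes: "The follow-up monthly seizure count is defined as the total number of observable focal onset seizures occurring during the follow-up period", multiplied by 28 over the number of follow-up days (X_FU). It reports the number and percentage of participants with "a seizure rate that is more than twice that of the baseline monthly seizure count". It also reports weekly counts by period, cluster seizures, and focal to bilateral tonic-clonic seizures that appear for the first time in follow-up.

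On medications, SAP Appendix 5 says: "Summaries of concomitant medications will be presented by ATC term, cohort and treatment group for the double-blind and open-label phases". Follow-up is not named, and SAP Appendix 9 lists no medications of special interest.

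**The concern.** The two rates being compared do not share a background treatment. The baseline rate is measured on fixed AEDs. The follow-up rate is measured on whatever AEDs the participant has by then, and AEDs may be added when required. A participant whose seizures rise after stopping is more likely than others to be given one, and that AED then lowers the rate being measured. Such a participant can be tabulated as not above twice baseline because the rise was treated.

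Uptake may also differ by arm. Early exits on seizure count enter this analysis if they decline the OLE. They plausibly need a new AED more often, and they may not be evenly split between JNJ-40411813 and placebo.

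The SAP calls these outputs safety findings. A reader of the planned tables could not tell an absent rise from a treated one.

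**Working it through.** The documents give no figure for this analysis, so there is nothing to reproduce. The check asks how far the written rule can be moved by a new AED.

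**Inputs from the documents:** 14 follow-up days; threshold of more than 2 × baseline; baseline of about 56 days scaled to 28; at least 3 seizures per 28 days at entry.

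**Assumptions, not in the documents:** rebound multiple *m*, number of follow-up days *d* before the new AED acts, and proportional cut *e* in the rate after that.

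**Expected ratio over all 14 days:** m × [d + (14 − d)(1 − e)] / 14.

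| m | d = 3, e = 30% | d = 3, e = 50% | d = 7, e = 30% | d = 7, e = 50% |
|---|---|---|---|---|
| 2.5 | 1.91 | 1.52 | 2.13 | 1.88 |
| 3 | 2.29 | 1.82 | 2.55 | 2.25 |

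A true 2.5-fold rate falls below the threshold on average in 3 of the 4 cases. A true tripled rate does so in 1 of 4.

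**Full return to baseline:** (m·d + 14 − d)/14 > 2 requires d > 14/(m − 1). That is 7 days for m = 3 and about 4.7 days for m = 4.

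**Chance of being counted as above twice baseline.** Simulation of 400,000 participants per setting: baseline count over 56 days halved, kept if at least 3; follow-up count over 14 days doubled. For a true baseline of 8 per 28 days, variance twice the mean, tripled rate:

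| Scenario | Counted |
|---|---|
| No new AED | 74% |
| Rate cut by 30% from Day 5 | 59% |
| Rate cut by 50% from Day 5 | 46% |
| Baseline fully restored from Day 5 | about 35% |
| Only the 5 days before the AED counted | 64% |

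Across true baselines of 4 to 30 per 28 days, Poisson or overdispersed, the no-AED figure is 56-97% and the full-restoration figure 24-36%.

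**Effect on a group.** With Poisson counts, baseline treated as known at 8, and 25% of rebounding participants starting an AED:

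- m = 3, d = 3, e = 50%: 0.75 × 84.5% + 0.25 × 30.9% = 71%, against 85% with no AED.
- m = 2.5, d = 7, e = 30%: 0.75 × 66.7% + 0.25 × 47.7% = 62%, against 67%.

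**Does cutting the count at the AED change solve it?** Not without a cost. Suppose there is no rebound and an AED starts once a 3-day count reaches about three times its expected value (an assumed trigger, no AED effect modelled; baselines 4, 8 and 15; Poisson or overdispersed). Among starters, the truncated count puts about 45-64% above twice baseline, against 10-28% with all days. Among starters with at least 7 days counted, the figures are about 20-37% against 9-23%.

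**The case against.** The strongest reply is that counting every follow-up seizure is a legitimate summary of what happens after stopping under usual care, and that the obvious alternative is biased too. Ending the count just before an AED that seizures prompted means stopping on the outcome, which inflates the rate. The calculation above bears this out, so truncation should not become the main rule. For the new tonic-clonic finding, truncation can only delete observed events from a safety table. An early cut also keeps mainly days that SAP 5.6.2 still counts as treatment-emergent for adverse events (last dose plus 5 days), so it could miss a later withdrawal effect.

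The size can fairly be questioned as well. Full reversal by Day 5 requires a rise to occur, be noticed, be treated and be abolished within days, while the only scheduled follow-up contact is the 2-week call. The by-week plot in SAP 5.5.2.2 separates follow-up week 1 from week 2, which gives partial protection. The summary is descriptive, with no test.

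Three stronger readings are tempting and are not supported:

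- That this is the trial's only planned look at rebound. The heading of SAP 5.5.2 and the exploratory objectives are blacked out, and adverse events are collected to the final visit.
- That the fall from 74% to 35% is the loss to expect. It applies only to an affected participant under a strong assumption.
- That every treatment change hides a rise. Protocol 6.7 does not limit the direction of change, and a reduced AED could mimic a rise. This point is confined to starts and increases.

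What the reply does not answer is visibility: no planned table shows who changed AED in follow-up.

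**Conclusion.** The concern holds in a limited form. The comparison in SAP 5.5.2.2 mixes stopping study drug with AED changes made in response to seizures, and the planned tables do not let a reader separate the two. Dilution below the threshold is arithmetically easy for an affected participant: 15 to 39 percentage points in the worked case (74% to between 59% and 35%). For the group it was 5 to 14 points at an assumed 25% uptake. The actual size cannot be stated, because uptake, AED effect and rebound size are not in the documents. The purpose of the section is read from Protocol 4.2 and from its three-period comparison, since its heading is blacked out; the sentence that defines the count is intact. The primary result is not affected. The change is worth making because it is cheap and decides whether a low count can be read as reassurance.

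**What to change.** In SAP 5.5.2.2:

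1. Keep the all-days counts as the main summary.
2. Report by arm and cohort the number and percentage of participants who start or increase an AED in follow-up, using the concomitant-medication dates already collected to the final visit. Split the threshold table into three rows: more than twice baseline; not more than twice, no AED change; not more than twice, AED started or increased. The last row should not be read as no rebound.
3. As a sensitivity analysis only, repeat the weekly counts and the threshold finding with seizures and X_FU cut at the day before the AED change. State that the cut depends on the outcome and inflates rates, with the size shown above under the assumed trigger.
4. Do not truncate the new focal to bilateral tonic-clonic finding. Mark whether each event came before or after the AED change.

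The cost is one derivation and a few more table rows. No new data are needed, and no change to the rules on AED use is proposed.
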